3.12.1.1 Drug-induced Liver Injury

Participants will be monitored for signs of drug-induced liver injury (DILI).

Potential events of DILI will be defined as meeting all the following criteria (as specified in the FDA Guidance for Industry: Drug-Induced Liver Injury: Premarketing Clinical Evaluation. [FDA, 2009]):

- ALT $> 4 \times$ ULN or aspartate aminotransferase $> 3 \times$ ULN
- No other reason can be found to explain the combination of laboratory value increases (e.g., acute viral hepatitis; alcoholic and autoimmune hepatitis; hepatobiliary disorders; nonalcoholic steatohepatitis; cardiovascular causes; concomitant treatments)

Potential events of DILI will be reported as SAEs. All participants with potential DILI will be closely followed until abnormalities return to normal or baseline or until all attempts to determine resolution of the event are exhausted.

3.12.2 Clinical Laboratory Assessments

Laboratory evaluations will be collected for hematology, coagulation, chemistry, urinalysis and other parameters. Refer to [Table 3-10](#).

Additional safety laboratory tests may be conducted as needed by the Investigator to evaluate participant safety.

Table 3-10: Clinical Laboratory Tests

Hematology	Coagulation	Chemistry	Urinalysis	Other
Hematocrit	International normalized ratio	ALT	Bilirubin	EPO
Hb	Prothrombin time	Albumin	Blood	FSH (post-menopausal females only)
RBC count	aPTT	Alkaline phosphatase	Glucose	Pregnancy - serum and urine (females only) ^b
Mean corpuscular volume		AST	Ketones	
Mean corpuscular Hb		Bicarbonate	Leukocytes	
Mean corpuscular Hb concentration		Blood urea nitrogen	Microscopic analysis of sediment if clinically indicated	Lipid Panel
Reticulocyte count (absolute and %)		Calcium	Nitrite	Amylase
Platelet count (estimate not acceptable)		Chloride	pH	Lipase
White blood cell count including differential count (percent and absolute):		Creatine phosphokinase	Protein	Hemoximetry
• Neutrophils		Creatinine	Specific gravity	RBC deformability and dense cells
• Lymphocytes		Fasting glucose	Urobilinogen	
• Monocytes		Lactate dehydrogenase		
• Basophils		Magnesium		
• Eosinophils		Phosphorous		
		Potassium		Serology Panel:
		Sodium		HIV 1/2 antibody
		Total bilirubin (direct and indirect)		Hepatitis A virus IgM antibody
		Total protein		Hepatitis B virus surface antigen
		Uric acid		Hepatitis C virus antibody
		eGFR ^a		SARS CoV-2
				Alcohol breath test

^a Using the Cockcroft-Gault formula.

^b Tests will be conducted at the clinic.

3.12.3 Vital Signs

Vital signs assessments will include respiratory rate (breaths per minute), systolic and diastolic blood pressure (BP) (mmHg), and heart rate (HR) (beats per minute [bpm]) and body temperature, which will be measured after a participant has rested for at least 5 minutes in the supine position. Any clinically significant abnormal vital sign assessment requires at least 1 repeat measurement.

Vital signs abnormalities that are (1) considered clinically significant initially and on confirmation, (2) require a participant to be discontinued from the study, (3) require a participant to receive treatment, or (4) require a change or discontinuation from the study drug (if applicable) will be recorded as AEs.

3.12.4 Electrocardiogram

Electrocardiogram (ECG) (12-lead) will be collected in triplicate within 5 minutes. The following ECG parameters will be recorded: HR, PR, QRS, QT, and QTcF intervals. ECGs will be collected at the time points in the schedules of assessments/procedures in [Table 3-1](#) to [Table 3-4](#).

For any ECG that the Investigator considers clinically significant, the Investigator will:

- Repeat the ECG.
- Follow-up ECG(s) will be obtained if any significant abnormalities are detected after dose administration to document resolution and as clinically indicated.
- Record as an AE any ECG that is 1) confirmed by the Investigator as clinically significant, 2) requires a participant to be discontinued from the study, or 3) requires a participant to receive treatment

3.12.5 Physical Examinations

A full physical examination will be conducted at Screening. All subsequent physical examinations should be signs and symptoms driven. Full physical examination will include examination of the following: general appearance, head, ears, eyes, nose, throat, neck, skin, cardiovascular system, respiratory system, gastrointestinal system, musculoskeletal system, lymph nodes, and nervous system ([Table 3-1](#) to [Table 3-4](#)).

An abnormal physical examination finding during the on-study period (i.e., following dose administration) that is considered clinically significant and (1) requires the participant to be discontinued from the study, or (2) requires the participant to receive treatment will be recorded as an AE.

3.12.6 Medical and Surgical History

Medical and surgical history will be collected at Screening and again at CRU admission to determine if any changes have occurred since screening.

3.13 Protocol Deviation Reporting

Procedural deviations found by the Clinical Research Associate (CRA) during monitoring visits and data deviations captured on the case report form (CRF) and found through programming and examining the database will be listed by participant.

4. CHANGES IN THE CONDUCT OF THE STUDY OR PLANNED ANALYSIS

All analyses specified in this SAP are consistent with the final study protocol (Version 6.0, Amendment 5 dated 08 March 2022). Any changes in this analysis provided or any additional analysis performed will be documented in CSR.

5. **QUALITY CONTROL AND QUALITY ASSURANCE METHODS FOR DATA ANALYSIS**

Case report forms will be monitored and processed according to the ICON Study Specific Procedure (SSP) DM-35070052.01 Data Management Plan (DMP). The DMP describes CRF data processing, edit checks, data query management, medical dictionary coding, SAE reconciliation, data transfers, and data quality review through database lock or any necessary reopening of the database. After database lock, the data will be retrieved from the database using SAS GRID Linux/SAS Studio - SAS® 9.4 version (or higher).

6. PHARMACOKINETIC AND PHARMACODYNAMIC ANALYSIS

6.1 Pharmacokinetic Analysis

Pharmacokinetic variables will be calculated from the RBC, plasma and whole blood concentration data for GBT021601 using non-compartmental methods CCI [REDACTED] and actual sampling times for single dose part only.

The following PK parameters will be determined for RBC, plasma and whole blood concentrations of GBT021601:

Single-dose parameter:

Term	Parameter	Description
C_{\max}	Maximum observed concentration	Observed peak concentration obtained directly from the experimental data without interpolation.
t_{\max}	Time to maximum observed concentration	Time corresponding to C_{\max} .
AUC_{0-24}	AUC from time 0 to 24 hr	Calculated by linear/log trapezoid rule. At 24 hr the last quantifiable concentration
AUC_{0-t}	Area under the concentration-time curve (AUC) from time 0 to the time of the last quantifiable concentration	Calculated by linear/log trapezoid rule.
$AUC_{0-\infty}$	AUC from time 0 to infinity	$AUC_{0-t} +$ the area extrapolated from the last quantifiable concentration to infinity (i.e., C_{last}/λ_z).
CL/F Apparent Oral Clearance	Dose/ $AUC_{0-\infty}$	Dose/ $AUC_{0-\infty}$
V_z/F	Apparent volume of distribution	Dose/($AUC_{0-\infty} * \lambda_z$)
$t_{1/2}$	Terminal phase (apparent elimination) half-life	$\ln(2)/\lambda_z$

The concentrations of GBT021601 in RBC will be derived using the following equation:

$$RBC\ Conc = \frac{Blood\ Conc - [(1 - Hematocrit) * Plasma\ Conc]}{Hematocrit}$$

The RBC concentration will be determined using individual hematocrit data collected on the day of PK sample collection. If hematocrit data are not available, the RBC value will be set to missing.

Only data points that describe the terminal elimination log-linear decline will be used in the regression equation for calculation of λ_z ; C_{max} and any data point in the distribution phase are not included in the calculation. A minimum of 3 points will be used for determination of λ_z . A general rule of adjusted $R^2 \geq 0.80$ will be considered as acceptable for calculation of λ_z . If adjusted R^2 falls below 0.80, then λ_z will be reported as Not Determined (ND) and that participant's values for λ_z , $t_{1/2}$, CL/F , V_z/F and $AUC_{0-\infty}$ will be reported in the appropriate listings but will be flagged and excluded from descriptive summaries and statistical analysis. If the extrapolated AUC_{inf} is more than 20%, then AUC_{inf} , CL/F and V_z/F will be listed but flagged and excluded from descriptive summaries and statistical analysis.

Blood to plasma ratios and RBC to plasma ratios for C_{max} and AUC will also be determined.

Multiple Dosing Period

Concentrations of GBT021601 in whole blood, plasma, and RBC will be listed for apparent C_{min} (minimum concentration from predose to 4 hours postdose) and C_{max} (maximum concentration from predose to 4 hours postdose) for each subject by visit and dose level. Descriptive statistics [n, arithmetic mean, SD, coefficient of variation (CV) %, geometric mean, and geometric mean CV%] will be summarized. For Part C, concentration data till Week 2 will not be summarized.

%Hb Occupancy

For both the SAD and MAD portions of the study the C_{max} (SAD) and apparent C_{min} and C_{max} (MAD) values will be used to calculate Hb occupancy with the following equation.

$$\% \text{ Hb occupancy} = \frac{[GBT021601]_{RBC}}{MCHC}$$

MCHC = mean corpuscular hemoglobin concentration; the MCHC value on the day of PK sample collection will be used. If MCHC value is not available, the % Hb occupancy value will be set to missing.

The % Hb occupancy of GBT021601 will be listed and summarized for each visit by treatment group, including n, arithmetic mean, SD, CV %, and in graphical format (linear scale [MAD only]).

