At the Week 13 Visit, eligible participants may be dose escalated to receive a loading dose and subsequent maintenance dose based on a predicted target of > 30% occupancy/modification. The mg dose and frequency will be determined by the PK results of GBT021601-011 and PK and hemoximetry results from Part A and Part B. Participants will receive maintenance doses through Week 16. Week 16 will be the end of treatment (EOT) Visit and participants will return to the clinical site for the end of Part B Safety Follow-up Visit approximately 5 half-lives (maximum of 120 days) after the final dose at the Week 16 Visit. The half-life will be determined from the PK results from the GBT021601-011 study and the PK results from Day 42 following the single dose (Part A) in this study. Participants will not be confined in the CRU during the Multiple Ascending-dose Period.

Extended Treatment Period (Part C)

As of Protocol Amendment 5, eligible participants may proceed with an Extended Treatment Period of at least 6 weeks, with a 300 mg loading dose twice daily over 4 days and subsequent maintenance dose of 150 mg once daily starting from Part C Day 1 and continuing through Part C Week 6. **CCI** [REDACTED]

Duration of Study Participation:

The maximum duration of the study is dependent on the half-life of GBT021601. At a minimum, the study duration will include a 28-day Screening period, an 8-week Single-dose Period, and a 6-week Multiple Ascending-dose Period for a total of 18 weeks. This will be followed by an EOB Visit 5 half-lives after the final dose of GBT021601. It is anticipated that 5 half-lives will not exceed 120 days after the final dose. Therefore, the maximum duration for a participant will be approximately 218 days or approximately 31 weeks.

As of Protocol Amendment 5, the maximum duration of the study will be approximately 53 Weeks, which includes the approximately 6-week Extended Treatment Period, and a 4- and 8-week follow up.

Number of Participants:

At least six (6) participants with SCD. Participants in Part A (single dose) will continue to Part B (multiple ascending-dose). As of Protocol Amendment 5, all eligible participants will proceed with the extended treatment period (Part C).

Participant Selection Criteria:

Participants with SCD ages 18 to 60 years, inclusive.

Test Product, Dose, Route of Administration, and Duration of Treatment:

Single-dose Period (Part A)

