ECGs, followed by vital signs, are to be taken before PK sampling unless PK samples will be late as a result

^a Week 8 (Day 56) is the first visit in the Multiple-Ascending-dose Period.

^b The Day 218 Visit will occur approximately 5 half-lives after the dose at Week 16.

^c HR, BP, RR, and body temperature will be measured after a participant has rested for at least 5 minutes in the supine position. Assessment of vital signs may be performed up to 3 hours predose.

^d 12-Lead ECG should be performed within 30 minutes prior to dose and will be collected in triplicate within 5 minutes after a participant has rested at least 5 minutes in the supine position.

^e Study drug will be administered as a loading dose of TBD mg and a maintenance dose of TBD mg every TBD (Dose 1) beginning at the Week 8 (Day 56) Visit. Participants will receive maintenance Dose 1 through Week 10. At the Week 8 Visit, the participant will remain in the clinic for 4 hours postdose for vitals, 12-lead ECG and AE assessment.

^f Study drug will be administered as a loading dose of TBD mg and a maintenance dose of TBD mg every TBD (Dose 2) beginning at the Week 13 (Day 91) Visit. Participants will receive maintenance Dose 2 through Week 16. At the Week 13 Visit, the participant will remain in the clinic for 4 hours postdose for vitals, 12-lead ECG and AE assessment

^g Site to dispense a new diary and collect the previous diary from the patient, when applicable. Diary to be collected only during the maintenance dosing when the participant is self-administering study drug at home. Participants should be instructed to complete the diary each week and return it at the next visit for site review.

^h A blood smear is to be performed before the Multiple Ascending Dosing Period Day 56 and Day 112 visits.

ⁱ The eGFR will be calculated using the Cockcroft-Gault formula.

^j A urine pregnancy test will be conducted. A serum pregnancy test will also be conducted when a positive urinary pregnancy test occurs for confirmation.

^k Samples for PK will be collected: predose, 0.25 to 1 hours postdose and 2 to 4 hours postdose. Sample collection times for hemoximetry and RBC deformability should be aligned with the predose PK sample and the 2 to 4 hour postdose PK sample. No 0.25 to 1 hour postdose sample shall be collected for hemoximetry or RBC deformability. The predose blood sample for PK and PD assessments should be collected within 30 minutes prior to dosing.

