4.3.2. Multiple Ascending-dose Period (Part B)

After a sufficient washout period (minimum of 56 days) and completion of a minimum of 4 participants in the Single-dose Period, the SMC will convene to review the safety, tolerability, and PK data from Day 42. If the SMC agrees to initiate the intrapatient multiple ascending dose portion of the study, participants will receive a maintenance dose regimen which may or may not be preceded by a loading dose at Week 8 (\pm 4 weeks). The initial loading dose and maintenance dose and frequency will be based on a predicted target of ~20% to 30% occupancy as determined by the PK results from the SAD part of Study GBT021601-011 in healthy participants and PK and hemoximetry results (occupancy/modification) from Part A. The maintenance dose will be administered through Week 10. Pharmacokinetics and % Hb occupancy will be evaluated following multiple dosing (first intrapatient dose escalation) in order to determine a dosing regimen for the second intrapatient dose escalation via modeling and simulation.

[figure not shown]
After the first multiple dose period, if the % Hb occupancy is higher than 30%, the participant may remain on the same maintenance dose or have a dose increase that exceeds the % Hb occupancy/modification of 30% based on the SMC recommendation. If the % Hb occupancy is less than 30%, the participant will dose escalate at Week 13.

At the Week 13 Visit, participants may receive a loading dose and subsequent maintenance dose based on a predicted target of > 30% occupancy/modification as determined by the PK and/or hemoximetry results of GBT021601-011 and Part A of this study. The maintenance dose will then be given Week 14 through Week 16 up to the end of treatment (EOT) Visit. Week 16 will be the EOT Visit and participants will return to the clinical site for the end of study (EOS) Visit approximately 5 half-lives after the final dose at Week 16. The half-life will be determined from the PK results from the GBT021601-011 study and Day 42 following a single dose of 100 mg. It is anticipated that 5 half-lives will not exceed 120 days after the final dose.

Participants will not be confined at the CRU during the Multiple Ascending-dose Period.

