8.1.1. Single-dose Period

During the Single-dose Period, plasma and whole blood PK samples will be collected at the following times:

Pre-dose (within 60 minutes of dosing) and postdose at 0.25, 0.5, 1, 2, 4, 6, 8, 12 hours; 24 hours (Day 2), 36 hours, 48 hours (Day 3), and 72 hours (Day 4); Days 7, 14, 21, 28, and 42.

The windows for sample collection are provided in [Table 10](#).

Table 10: Windows for PK Sample Collection – Single-dose Period

Sample Collection Time	Allowed Deviation
0.0 – 1.0 hour	± 2 minutes
> 1.0 – 24.0 hours	± 5 minutes
> 24.0 – 72.0 hours	± 10 minutes
> 72.0 – 144.0 hours	± 15 minutes
> 144.0 hours	± 24 hours

Blood samples for hemoxygometry and RBC deformability, dense cells will be collected at the same time as the PK samples at pre-dose and 12 hours postdose on Day 1. In addition, hemoxygometry samples will be collected on Days 2, 4, 7, 21, and 42.

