8.1.2. Multiple Ascending-dose Period

Plasma and whole blood pre-dose and postdose PK samples will be collected in the Multiple Ascending-dose period as listed in [Table 11](#). Whole blood samples for hemoxygometry and RBC deformability, dense cells will be collected at the same time as the PK samples.

Table 11: PK and PD Sample Collection Times – Multiple Ascending-dose Period

Week	Pre-dose ^a	Postdose
8	1 PK/PD sample Pre-dose	1 PK sample between 0.25 hour to 1 hour 1 PK/PD sample between 2 to 4 hours
9	1 PK/PD sample Pre-dose	1 PK sample between 0.25 hour to 1 hour 1 PK/PD sample between 2 to 4 hours
10	1 PK/PD sample Pre-dose	1 PK sample between 0.25 hour to 1 hour 1 PK/PD sample between 2 to 4 hours
11	1 PK sample Pre-dose	1 PK sample between 0.25 hour to 1 hour, 1 PK/ sample between 2 to 4 hours
12	1 PK sample Pre-dose	1 PK sample between 0.25 hour to 1 hour 1 PK sample between 2 to 4 hours
13	1 PK/PD sample Pre-dose	1 PK sample between 0.25 hour to 1 hour 1 PK/PD sample between 2 to 4 hours
14	1 PK sample Pre-dose	1 PK sample between 0.25 hour to 1 hour 1 PK sample between 2 to 4 hours
15	1 PK sample Pre-dose	1 PK sample between 0.25 hour to 1 hour 1 PK sample between 2 to 4 hours
16 EOT	1 PK/PD sample Pre-dose	1 PK sample between 0.25 hour to 1 hour 1 PK/PD sample between 2 to 4 hours
EOS/ET	Anytime during visit	

Abbreviations: PD, pharmacodynamics; PK, pharmacokinetics.

^a The pre-dose blood sample for PK and PD assessments should be collected within 30 minutes prior to dosing.

Table 12: PK and PD Sample Collection Times –Extended Treatment Period CCI

Extended Treatment Period		Pre-dose ^a	Postdose
Week	Day		
1	1	1 PK/PD sample	1 PK sample between 0.25 hour to 1 hour 1 PK/PD sample between 2 to 4 hours
2	15	1 PK/PD sample	1 PK sample between 0.25 hour to 1 hour 1 PK/PD sample between 2 to 4 hours
4	29	1 PK sample	1 PK sample between 0.25 hour to 1 hour 1 PK sample between 2 to 4 hours
6	43	1 PK sample	1 PK sample between 0.25 hour to 1 hour 1 PK sample between 2 to 4 hours
10	71	1 PK sample	
14	98	1 PK sample	
Final Visit	Anytime during visit		

Abbreviations: PD, pharmacodynamics; PK, pharmacokinetics.

^a The pre-dose blood sample for PK and PD assessments should be collected within 30 minutes prior to dosing.

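### If a participant's half-life exceeds about 18 days (about 12 for red cells), the SAP's 20% rule drops single-dose AUCinf, CL/F and Vz/F from the summaries, and the plan does not say whether the Week 8 predose sample may be used

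*SAP*

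**What the plan says.** SAP 6.1 limits the non-compartmental analysis to the single-dose part. If more than 20% of AUCinf is extrapolated, AUCinf, CL/F and Vz/F "will be listed but flagged and excluded from descriptive summaries and statistical analysis". Half-life is not touched by this rule; only the separate adjusted R² rule can remove it.

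Protocol 8.1.1 sets the later Part A samples at "24 hours (Day 2), 36 hours, 48 hours (Day 3), and 72 hours (Day 4); Days 7, 14, 21, 28, and 42". RBC concentration is derived in SAP 6.1 from blood, plasma and same-day hematocrit, and is missing without that hematocrit. Protocol Table 1 schedules post-dose hematology only on Days 2, 4, 14 and 28.

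At Week 8, Protocol Table 11 lists "1 PK/PD sample Pre-dose", and Table 3 schedules hematology at the same visit. The participant has then had only the Part A dose. Neither document says whether that sample may be used in the Part A analysis.

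No half-life is stated. Two planning figures bear on it. Protocol Table 3, footnote b: "The Day 218 Visit will occur approximately 5 half-lives after the dose at Week 16". Protocol 4.3.2: "It is anticipated that 5 half-lives will not exceed 120 days after the final dose".

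**The concern.** Single-dose PK is a secondary objective, and SAP 7.16 promises summary statistics for the single-dose parameters. If the drug is eliminated slowly, Day 42 is too early to keep the tail under 20%, and three parameters lose some or all of their summaries.

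The rule works participant by participant. The extrapolated share rises with half-life, so with about six participants the slowest eliminators are removed first. For a given volume of distribution, the summarised CL/F would then be too high. The sample that would reduce the loss is already scheduled.

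**Working it through.** **The plan's own duration figure.** The synopsis says "the maximum duration for a participant will be approximately 218 days or approximately 31 weeks". Its periods are "an 8-week Single-dose Period, and a 6-week Multiple Ascending-dose Period for a total of 18 weeks", including 28 days of screening. Leaving screening out, 56 + 42 + 120 = 218 days = 31.1 weeks, an exact match. So 218 can be rebuilt from the 120-day ceiling. Measured from Week 16 (Day 112), as footnote b does, 218 − 112 = 106 days.

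**Half-lives to try (all assumptions).**
- Footnote b: 106/5 = 21.2 days.
- Ceiling: 120/5 = 24 days, an upper bound.
- The 56-day washout in Protocol 4.3.2, if it were five half-lives: 56/5 = 11.2 days.
- Loading-to-maintenance ratios, if the loads were meant to reach steady state: 500/50 = 10 (Protocol 3.3.2) and 2400/150 = 16 (Protocol 4.3.3). With t½ = ln 2 / −ln(1 − 1/ratio), these give 6.6 and 10.7 days.

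**Elapsed time.** Day 1 is the dosing day (24 hours is Day 2), so Day 28 is 27 days after dosing, Day 42 is 41 and Day 56 is 55. The end of the Week 8 window in Table 3 (Day 56 + 4 weeks, Day 84) is 83.

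**Extrapolated share.** For a mono-exponential decline, share = 2^(−T/t½), and the 20% limit is crossed at t½ = T × ln 2 / ln 5 = 0.4307 × T.

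| Assumed t½ (days) | Plasma and blood, T = 41 | RBC, T = 27 | With Week 8 at Day 56, T = 55 | With Week 8 at Day 84, T = 83 |
|---|---|---|---|---|
| 11.2 | 7.9% | 18.8% | 3.3% | 0.6% |
| 15 | 15.0% | 28.7% | 7.9% | 2.2% |
| 21.2 | 26.2% | 41.4% | 16.6% | 6.6% |
| 24 | 30.6% | 45.9% | 20.4% | 9.1% |
| 20% crossed above | 17.7 d | 11.6 d | 23.7 d | 35.7 d |

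Counting Day 42 as 42 days changes little: 25.3% and 29.7% at 21.2 and 24 days, with the limit crossed at 18.1 days. Counting Day 56 as 56 days gives 19.8% at 24 days, so that case sits on the limit either way.

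**Check with a distribution phase.** A simulated non-compartmental analysis used the Part A sampling times, linear-up/log-down trapezoids and the last four points for λz. It assumed a 2-hour absorption half-life and a fast phase of 2-day half-life making up 0, 25 or 50% of the initial concentration. At Day 42 it gives 23.6–26.3% (21.2 days) and 27.9–30.7% (24 days). With Day 56 added it gives 15.1–16.6% and 18.8–20.5%.

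**AUC ratios.** SAP 6.1 plans RBC-to-plasma AUC ratios without naming the AUC. If AUC0-t is used, RBC stops at 27 days and plasma at 41. The mismatch multiplies the ratio by (1 − 2^(−27/t½)) / (1 − 2^(−41/t½)):
- 11.2 days: 0.812/0.921 = 0.88, about 12% too low.
- 21.2 days: 0.586/0.738 = 0.79, about 21% too low.

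**The case against.** A reader might infer that the protocol implies a half-life of 21 to 24 days and that the three parameters will therefore be dropped. The documents do not support that. The 24 days come from a ceiling, and Day 218 can be rebuilt from the same ceiling, although footnote b does tie it to about five half-lives. Other figures point lower. The protocol treats 56 days as sufficient washout, yet at 21.2 to 24 days 16 to 20% would remain (2^(−56/21.2) and 2^(−56/24)). The loading ratios suggest about 7 to 11 days. In that range plasma and whole blood are unaffected. This objection stands, and it is why the point is conditional.

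The loss is also limited. The values stay in the listings, and the 20% rule leaves Cmax, tmax, AUC0-24, AUC0-t and half-life in the summaries. Protocol 11.5 allows population PK, and Protocol 3.4.2.3 reports a model on all six participants. That stands too, but SAP 6.1 specifies only non-compartmental analysis for the single-dose parameters.

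Nor should the Week 8 sample be read as a full cure. At 24 days a Day 56 draw still leaves about 20%. No quantification limit is given, so the value may not be measurable. The last sampling time would run from Day 56 to Day 84 between participants.

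For RBC, the same-day hematocrit rule also leaves Day 1 without post-dose values, because no hematology is scheduled that day. Week 8 does not repair that.

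**Conclusion.** The point holds conditionally. If a participant's half-life exceeds about 18 days, AUCinf, CL/F and Vz/F in plasma and whole blood leave the summaries. At 21.2 to 24 days about 26 to 31% would be extrapolated; at about 11 days, about 8%, and nothing is lost.

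The RBC part is firmer. The limit is crossed above about 11.6 days, 18.8% is extrapolated even at 11.2 days, and 41 to 46% at 21.2 to 24 days.

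These figures assume a mono-exponential tail, scheduled visits only, and Day 1 as time zero. The change is worth making because it costs little, settles an analyst's choice in advance, and limits exclusions that depend on the quantity being estimated. It does not show that the single-dose PK objective fails as planned.

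**What to change.** In SAP 6.1:

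- Pre-specify that the Week 8 predose concentration is the last point for λz and AUCinf, and hence CL/F and Vz/F, in plasma, whole blood and RBC. Use its actual time, require that it precede the first Part B dose and be quantifiable, and use that day's hematocrit for RBC.
- Report a partial AUC over a common interval: to Day 42 for plasma and whole blood, and to Day 28 for RBC. This keeps participants comparable when the Week 8 time varies.
- Compute RBC-to-plasma AUC ratios over the same interval in both matrices.

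The cost is a few SAP sentences and some programming, with no new sample or visit. The downside is the varying last sampling time, which the partial AUC addresses. The missing Day 1 RBC values remain a separate gap.
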